**PLACEBO**

INDICATION The Medical Device is a nasal spray indicated in adults over 18 years in the treatment of nasal symptoms of acute rhinitis and rhinosinusitis, reduces swelling of the nasal mucosa.	UNDESIRABLE EFFECTS Feeling of itching and irritation can occur while initiating the treatment. In case of undesirable effects, contact your doctor.
COMPOSITION Isotonic saline solution (salinity 0.9%)	STORAGE AND WASTE RECOMMENDATION Store at room temperature and not above 30°C. See the expiry date on the box or the bottle. Ask your pharmacist to throw out the bottle after use. These measures contribute to protect the environment.
DIRECTION OF USE One-two sprays twice a day in each nostril for 7 days or as recommended by your doctor or pharmacist.	TECHNOLOGY The spray pump APF (Advanced Preservative Free) uses a technology that permits to dispense a preservative free solution.
PRECAUTION OF USE - Keep out of reach of children. - If symptoms persist more than 7 days, ask for advices to your doctor or pharmacist. - The bottle shall be used by only one person for hygiene reason and to avoid the transmission of pathogenic agents that could be in contact with the nozzle.	HOW TO USE HEALSEA® PLACEBO? 1. Place the nozzle smoothly into the nostril while keeping head straight. 2. Once the nozzle is placed, press on the nozzle in each nostril. Let flow the excess of solution and wipe. 3. Clean the nozzle with tissue, soapy water, rinse and dry after every use.
CONTRAINDICATION Do not use in children and adolescents under 18 years. Do not use in case of hypersensitivity or allergy to one or several components.	

Lallemand Pharma AG  
[name]  
[name]  
Switzerland

EC REP

ASPE CONSEIL  
[name]  
[name]

**Appendix B: Primary Notification Form**

**This form is to be completed immediately and no later than 24h (in case of any SERIOUS safety issue) or 48h (in case of any NON-SERIOUS safety issue).**

Protocol title: [to be completed]	Acronym: [to be completed]									
Sponsor code: [to be completed]	Site number: 

 	 	 	 	

 Country:									
Competent authority(ies) reference number: [to be completed]	Transmission date: 

 	 	 	 	 	 	 	 	ddmmyy	

									ddmmyy
								ddmmyy		

1. Date, type and classification of incident report													
Incident codification:	First notification: 	Follow-up: 	Final: 										
Date of the incident	

 	 	 	 	 	 	 	 	ddmmyy	

									ddmmyy			
								ddmmyy					
Reporter awareness date	

 	 	 	 	 	 	 	 	ddmmyy	

									ddmmyy			
								ddmmyy					
Classification/type of the incident	 Serious public health threat  Unanticipated serious deterioration in state of health  Death  Non serious incident  Expected undesirable side effect												

2. Patient information																														
Birthdate: 

 	 	 	 	 	 	 	 	mmyyyy	

									mmyyyy	Gender: Male  Female  Unknown  Non applicable 																				
								mmyyyy																						
Height: 

 	 	 	 	 	 	 	 	cm	

									cm	Weight: 

 	 	 	 	 	 	 	 	,	 	 	 	 	 	 	 	kg	

									,								kg			
								cm																						
								,								kg														
List any of the patient's prior condition of medication that may be relevant to this incident:																														

*Strictly Confidential*

3. Medical Device information		
UDI device identifier / Eudamed ID:  not applicable	Basic UDI-DI/Eudamed-DI:  not applicable	UDI production identifier:  not applicable
Medical device name (brand, trade, proprietary or common name) & SKU:		
Class of risk:		
Batch number		
Expiry date (yyyy/mm):		
Other details:		
4. Incident information		
Intended use of the medical device:		
Date of first use:	   ddmmyy	
Date of last use:	   ddmmyy	
Frequency of use: _____		
Description of the incident: Provide a comprehensive description of the incident, including (1) what went wrong with device (if applicable) and (2) a description of health effects (if applicable), i.e. clinical signs, symptoms ...):		
Outcome & Health Impact:		
 death  life threatening  hospitalization (initial or prolonged)  required intervention to prevent permanent damage  disability or permanent damage  congenital abnormality/birth defect   no serious outcome   other, please specify: _____		
Remedial actions taken by investigator, patient, or user subsequent:		

*Strictly Confidential*

**5. Reporter information**

- Distributor
- Patient
- Healthcare professional: \_\_\_\_\_
- Investigator (*in case of the safety issue has been occurred during a clinical investigation*)
- Other, please specify: \_\_\_\_\_

For any follow-up please kindly indicate the contact details:

Name and Surname: \_\_\_\_\_

Email: \_\_\_\_\_

Phone number: \_\_\_\_\_

Fax: \_\_\_\_\_

Date:

Signature:

\_\_\_\_\_

\_\_\_\_\_

**Appendix C: SAE form**

This form is to be used when a causal relationship between the serious adverse event and the additional investigational procedure is suspected (art 80.5 and 80.6).

This form is to be completed immediately and no later than 3 days after the investigation site personnel have been made aware of the event and sent immediately to the Clinical Study Monitor by mail [contact] and to BG Clinicals [[contact]](mailto:[contact]), FAX: no [contact], to the sponsor [[contact]](mailto:[contact]) and/or [contact] (as back-up method) and to the Vigilance Manager [name] ([[contact]](mailto:[contact])) and the EU representative ([[contact]](mailto:[contact])).

Protocol title: Efficacy and safety of Healsea® hypertonic nasal spray 2.7 % in the treatment of acute infectious rhinitis in adults	Acronym: TEACHER			
Sponsor code: LPH-2201	Competent Authority(ies) reference number:			
Transmission date: 

 	 	 	

 ddmmyy				

SAE# (to be completed by the sponsor)	First notification: 	Follow-up: 	Final: 
--	--	-------------------------------------	---------------------------------

1. Subject information													
Birthdate: 

 	 	 	 	 	 	

 mm/yyyy							Gender: Male  Female  Other 						
Height: 

 	 	 	 	

 cm					Weight: 

 	 	 	 	

 , 

 	 	

 Kg								
Investigational arm:	 Healsea® Rescue	 Placebo	 blinded										

2. Description of the SAE	
The serious adverse event resulted in:	 Medical or surgical intervention to prevent life threatening illness or injury or permanent impairment to a body structure or a body function  Chronic disease  Foetal distress, foetal death or congenital physical or mental impairment or birth defect
 Death (whatever may be the cause)	
Serious deterioration in the health of the subject, that resulted in any of the following:	
 In-patient hospitalisation or prolongation of existing hospitalisation (*)	
 Life threatening illness or injury	
 Permanent impairment to a body structure or a body function	

Description of the SAE: (if clinical nature, indicate the diagnosis or the major symptoms)

*Strictly Confidential*

### 3. Measures taken following the SAE

## The event led to:

Prescription of corrective or symptomatic medication / medical device (specify name, dosage):  
.....

Other, specify:

#### 4. Outcome

 Not recovered/Not resolved	 Recovering/Resolving	 Recovered/Resolved
 Recovered/Resolved with	 Unknown	
sequelae  Fatal: in case of death, has an autopsy been conducted?  Yes  No		

5. Investigator causality assessment with the study procedure (investigator's assessment to be done as soon as possible)

Not related    Possible    Probable    Causal relationship

### Comments:

---

Page 10 of 10

---

10

*Strictly Confidential*

Investigator

Other, please specify: \_\_\_\_\_

Name: \_\_\_\_\_

e-mail: \_\_\_\_\_

Phone number: \_\_\_\_\_

Fax: \_\_\_\_\_

Date:                       ddmmyy

Signature: \_\_\_\_\_

## LIST OF ABBREVIATIONS

AE:	Adverse Event
ATC:	Anatomical Therapeutic Chemical Classification
AUC:	Area Under the Curve
CI:	Confidence Interval
COVID-19:	Coronavirus Disease 2019
CRF:	Case Report Form
CRO:	Contract Research Organisation
Dx:	Day x
[E]:	Number of events
FAS:	Full Analysis Set
ICH:	International Conference on Harmonisation
LOCF:	Last Observation Carried Forward
MedDRA:	Medical Dictionary for Regulatory Activities
NSAID:	Non-Steroidal Anti-Inflammatory Drugs
PMCF:	Post-Market Clinical Follow-up
PP:	Per Protocol
PT:	Preferred Term
Q1 / Q3:	First / Third Quartile
SAS®:	Statistical Analysis System
SD:	Standard deviation
SOC:	System Organ Class
TEAE:	Treatment-Emergent Adverse Event
Vy:	Visit y
WHO-DRUG:	World Health Organization Drug Dictionary
WURSS-21:	Wisconsin Upper Respiratory Symptom Survey – Short version

## 1. INTRODUCTION

This statistical analysis plan is based on protocol LPH-2201 – version 1, dated on October 3rd, 2022. It defines populations of analysis and the evaluation methods of the principal and secondary criteria.

## 2. STUDY OBJECTIVES

### 2.1. Primary objective

The primary objective is to compare the efficacy of Healsea® Rescue\* and Placebo to improve the Quality of Life through symptoms of acute infectious rhinitis reduction in adults during a 7-day treatment period.

### 2.2. Secondary objectives

The secondary objectives are:

- To compare the efficacy of Healsea® Rescue\* and of the Placebo to reduce the duration of each infectious rhinitis symptoms rated by the short version of the Wisconsin Upper Respiratory Symptom Survey (WURSS-21);
- To compare the efficacy of Healsea® Rescue\* and of the Placebo to reduce the use of concomitant medication (antipyretics, systemic or local mucolytics, decongestants, antitussives, antibiotics);
- To compare the subject overall assessment on efficacy of Healsea® Rescue\* and of the Placebo;
- Safety: to assess systemic and local tolerance of Healsea® Rescue\* over the study period.

## 3. STUDY DESIGN

This is a prospective, interventional, double-blinded, placebo controlled, randomized, national (Bulgaria), monocentric PMCF study.

Investigational plan description (see Figure 1):

#### - Visit 1 (V1) - (Day 1): Screening/Inclusion/Randomization

Information and consent, demographic data and medical history, ongoing medication, physical and clinical examination (including COVID-19 antigen test), inclusion/non-inclusion criteria, randomization, e-diary presentation (including the first study questionnaire completion), reporting of adverse events, dispensation of Healsea® Rescue\* Nasal Spray or Placebo (Isotonic nasal spray) (according to randomization list).

#### - Day 1 (D1) - Day 8 (D8) (at home):

Daily completion of the electronic diary (questionnaire, adverse events/incidents and concomitant medications), Healsea® Rescue\* /Placebo nasal spray treatment daily administration.

- **D8 (Telephone call):**

End of Healsea® Rescue\*/Placebo nasal spray treatment.

- **Day 9 (D9) - Day 13 (D13)/Day 15 (D15) (at home):**

Daily completion of the electronic diary (adverse events/incidents, concomitant medications, WURSS-21 if applicable, until the subject feels not sick for two consecutive days).

- **Visit 2 (V2) (D13/D15): end of study**

Physical and clinical examination (including COVID-19 antigen test), diary review, reporting of adverse events and incidents, compliance, subject satisfaction, WURSS-21 completion if the patient has not ticked “not sick” for 2 consecutive days in the previous days.

The maximal study duration for each patient is 15 days.

	Acute phase		Telephone call	Follow-up	
	Screening/Inclusion	At home		At home	End of study
Visit name	V1		TC1	V2	
Visit Number				D9-End of study visit	
Days/Weeks	D1	D1-D8	D8	D13-D15	
Informed consent	X				
Eligibility criteria	X				
Demography and Medical history	X				
Physical and clinical examination	X				X
COVID-19 antigen test	X				X
Ongoing medication	X				
Randomization	X				
Treatment (Healsea® Rescue* or Placebo) (14 intakes)		X			
Telephone call (End of Healsea® Rescue* or Placebo)			X		
Subject e-diary and WURSS 21	X*	X		X §	X*
(Serious) Adverse Events/ (serious) incidents and concomitant medication reporting	X	X		X	X
Satisfaction Questionnaire					X
Compliance					X

§ After D8, WURSS-21 until complete resolution of symptoms for 2 consecutive days.

\*WURSS-21 to be completed with the investigator on site at screening and at the end of the study if the patient still has not ticked “not sick” for 2 consecutive days in the previous days.

**Figure 1 : Flow chart of the study**

## 4. SAMPLE SIZE

A sample of 180 subjects (90 subjects per group) will be needed to provide 80% power with a one-sided test at a 0.05 significance level to detect a difference between Healsea® Rescue\* and Placebo groups AUC of 30%.

Assuming that approximately 10% of subjects may drop-out the study, 200 subjects will be randomly assigned at a ratio 1:1 to Healsea® Rescue\* and Placebo (100 subjects per group).

## 5. DEFINITION OF THE ANALYSIS SETS

Screened patients: all patients who signed an informed consent.

Included subjects: all screened subjects who participated in the study.

Randomised patients: all patients who signed an informed consent and who were assigned a treatment number.

Safety Set: all the randomised patients who took at least one puff of the nasal spray.

Full Analysis Set (FAS): all the randomised patients who took at least one puff of the nasal spray and with at least one post-baseline efficacy data.

*Any patient not satisfying major entry criteria or for whom post randomisation data are not available will be identified by the Validation Committee during the data review, and could be excluded from the FAS in agreement with circumstances exposed in the ICH-E9 §5.2.1.*

Per-Protocol (PP) Set: Efficacy population based on the FAS without patients with major protocol deviations.

*The status of protocol deviations (minor or major) will be validated during the data review meeting.*

Safety endpoint will be performed on the Safety Set.

The analyses of primary and secondary endpoints will be performed on the FAS.

The primary endpoint will also be analysed on the PP set, analyses on the PP set being supportive in superiority trials. It will also be the case for one secondary endpoint (analysis of the AUC of the items 2 to 11 and 12 to 20 of the WURSS-21 questionnaire).

## 6. STATISTICAL METHODS

### 6.1. Data processing

The analyses will be computed with SAS Version 9.4 TS Level 1M6 Copyright (c) 2016 by SAS Institute Inc., Cary, NC, USA.

### 6.2. Description

The number of available data and the number of missing data will be given and the following descriptive statistics will be provided:

- For quantitative parameters: mean, standard deviation, median, Q1, Q3, extreme values (min and max).

In this case, calculated statistics (mean, standard deviation, median, Q1, Q3) will generally be displayed with one more significant figure than the observed data, unless the described variable necessitates less precision.

- For qualitative parameters: number and percentage of each modality.

Usually, one decimal digit will be given. A second decimal digit could be provided to improve the display, if required.

### 6.3. Statistical/Analytical issues

#### 6.3.1. Significance level

All statistical analyses will be performed at the 0.05 global significance level (type I error rate), using one-sided tests.

The statistical results are conclusive for the primary efficacy criterion.

All the other statistical results have to be considered within a descriptive perspective and not as inferential issues. No adjustment for Type I error is done. P-values of statistical tests will be provided for information only.

#### 6.3.2. Interim analysis

No interim analysis will be performed.

#### 6.3.3. Handling of dropouts and missing data

##### *a) Repositioning of visits*

Not applicable.

***b) Partially filled scales and missing data (other than WURSS-21 questionnaire and dates)***

Concerning dates and WURSS-21 questionnaire, see §6.4.

No imputation will be done. Missing data will not be estimated and will be treated as missing data for the statistical analysis.

***c) Dropouts***

Subjects from Full Analysis Set who prematurely discontinued the study will be included in the analysis.

Except for WURSS-21 questionnaire and dates, no method will be applied to replace missing data.

**6.4. General conventions and calculated variables****6.4.1. Subject reference start/end dates**

For each subject, the reference dates will be the following:

- The reference start date is the date of inclusion visit.
- The reference end date is the date when subject was determined to have ended the trial.

**6.4.2. Computation of a duration**

The formulae below will be generally used:

- Duration (in days) = Date#2 – Date#1 + 1 day

**6.4.3. Missing dates of inclusion visit or end of study**

Missing dates of inclusion visit and of end of study will be reviewed by the members of the Validation Committee and extrapolated using all information recorded.

#### **6.4.4. Missing start/end dates of adverse events / incidents / expected side effects**

In the following paragraphs, adverse events, incidents and expected side effects will be referred to as “adverse events” for ease of reading.

##### ***a) Start date***

Completely missing date: it will be estimated by the reference start date.

If the day and the month are missing:

- If the year = year of reference start date, it will be estimated by the reference start date
- If the year < year of reference start date, it will be estimated by the 31st December
- If the year > year of reference start date, it will be estimated by the 1st January

If only the day is missing:

- If the month/year = month/year of reference start date, it will be estimated by the date of reference start date
- If the month/year < month/year of reference start date, it will be estimated by the last day of the month
- If the month/year > month/year of reference start date, it will be estimated by the first day of the month

If after imputation, the estimated start date is after the end date of the adverse event, it will be replaced by the end date of the adverse event.

##### ***b) End date***

Note: the following rules concern events that are not “ongoing” at the end of the study.

Completely missing date: it will be estimated by the reference end date

If the day and the month are missing:

- If the year = year of reference end date, it will be estimated by the reference end date
- If the year < year of reference end date, it will be estimated by the 31st December
- If the year > year of reference end date, it will be estimated by the 1st January

If only the day is missing:

- If the month/year = month/year of reference end date, it will be estimated by the reference end date
- If the month/year < month/year of reference end date, it will be estimated by the last day of the month
- If the month/year > month/year of reference end date, it will be estimated by the first day of the month

---

If after imputation, the estimated end date is before the start date of the adverse event, it will be replaced by the start date of the adverse event.

#### **6.4.5. Missing start/end dates of concomitant medications**

Same rules as for adverse events.

#### **6.4.6. Scores of WURSS-21 questionnaire**

To compute scores of WURSS-21 questionnaire, if the questionnaire has been completed at a given time point except some items, these missing answers will be imputed by the last observation carried forward (LOCF).

At time-points the questionnaire has not been completed at all, no imputation will be done and the scores will be missing.

#### **6.4.7. AUC on scores of WURSS-21 questionnaire**

The computation of the AUC on any score of the questionnaire will be made for patients with non-missing value at D1 and at least another non-missing time point between D2 and D8. Otherwise, the AUC will be missing.

The AUC will be computed by the trapezoidal rule from D1 to D8 (Acute Phase).

If the value at D8 is missing, then it will be estimated by the value at the last non-missing time point before D8.

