#### 7.1.3 Primary Endpoint with methods and timing for assessing recording and analysing variables

**The AUC of Wisconsin Upper Respiratory Symptom Survey (WURSS-21) during first 8 days of symptoms will be compared between both groups.**

WURSS-21 is a validated 3-dimensional structure questionnaire [12]. This survey has been demonstrated to be responsive, and valid to assessing the severity and functional impact of the common cold. It includes 10 items assessing symptoms (symptoms score, (items 2 to 11), 9 items assessing functional impairments (quality of life score, (items 12 to 20).) and 2 items assessing respectively global severity and global change. Brown et al. [13] support the practice of using, for AUC computation, a simply summed daily global illness severity score to represent the overall symptomatic and functional impairments arising from acute upper respiratory infection.

The WURSS-21 will be assessed in an e-diary once daily in the evening, taking into account the symptoms from the morning to the evening, during D2-D8 (day of the end of treatment). At D1, the WURSS-21 will be completed during the visit. After D8, the WURSS-21 will be assessed once daily until the subject feels not sick for two consecutive days.

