**D9-D13/15 (at home):**

Patients will continue to complete the electronic diary daily (incidents/adverse events in relation with the common cold, concomitant medications). The patient for whom common cold symptoms persist, will be instructed to continue to complete the WURSS-21, until the subject feels not sick for two consecutive days.

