## **8.9 Management, justification, and documentation of missing data, including drop-outs**

Missing data for the primary endpoint (WURSS-21) will be estimated by interpolation.

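### SAP 6.4.7 carries the last score forward to a missing D8 even when a score soon after D8 exists; Protocol 8.9 specifies interpolation and SAP 12 does not declare the departure (minor)

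*SAP*

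**What the plan says.** Protocol 8.9 has a single rule for the primary endpoint: "Missing data for the primary endpoint (WURSS-21) will be estimated by interpolation". It names no interpolation method and gives no rule for a patient with no later score.

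The SAP splits the matter in two. For a day with no questionnaire, SAP 6.4.6 says: "At time-points the questionnaire has not been completed at all, no imputation will be done and the scores will be missing". SAP 6.4.7 then applies the trapezoidal rule from D1 to D8 and adds, for the end of the window: "If the value at D8 is missing, then it will be estimated by the value at the last non-missing time point before D8". An AUC is computed for any patient with a "non-missing value at D1 and at least another non-missing time point between D2 and D8".

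Scores after D8 are collected. Protocol 7.1.3 states: "After D8, the WURSS-21 will be assessed once daily until the subject feels not sick for two consecutive days". Protocol 7.4.1 repeats the instruction for patients whose symptoms persist. Under SAP 13.3, a patient who has already marked two successive days as not sick during treatment stops the questionnaire, so for that patient D8 is blank by design and normally no later score follows.

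SAP 12, which lists changes to the planned analysis, covers only the definition of symptom duration.

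**The concern.** Take a patient who misses D8 but fills in D9. The missing day is bracketed by two observed scores, so the protocol's rule can be applied as written. The SAP ignores the later score and holds the curve flat from the last earlier one. The SAP is also uneven within itself. A gap inside D1-D8 is bridged by a straight line, because the trapezoid simply joins the observed days, while a gap of the same length that includes D8 is held level.

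At stake is the derivation of the only endpoint that SAP 6.3.1 treats as conclusive. Two analysts, one following each document, would obtain different primary values for the same patient, and a reader of SAP 12 would not learn of the choice.

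**Working it through.** **The plan's own figures.** The documents give no expected AUC and no rate of missing D8 scores. The only related figure is the sample size (Protocol 8.5, SAP 4): 90 per group, 80% power, one-sided 0.05, 30% difference in AUC. The dropout step checks: 180/0.90 = 200. The 180 itself cannot be reproduced, because no SD is stated. Solved backwards, the standardised effect is (1.645 + 0.842) × √(2/90) = 0.371, which implies a coefficient of variation of 0.30/0.371 ≈ 0.81.

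**Error for one patient.** Let the last k days up to D8 be missing, with last score *a* on day 8 − k and score *b* on D9.
- Carry-forward area over the gap: k × a.
- Interpolated D8: a + (b − a) × k/(k + 1). Area: k × a + (b − a) × k²/[2(k + 1)].
- Carry-forward minus interpolation: (a − b) × k²/[2(k + 1)]. The multiplier is 1/4, 2/3 and 9/8 for k = 1, 2 and 3.

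**Assumed linear course: 60 at D1, falling 6 per day, D9 = 12.** True AUC = 7 × (60 + 18)/2 = 273, and interpolation returns 273 in every row.

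| Missing | a | Excess | Carry-forward AUC | Error |
|---|---|---|---|---|
| D8 | 24 | 12 × 1/4 = 3 | 276 | +1.1% |
| D7-D8 | 30 | 18 × 2/3 = 12 | 285 | +4.4% |
| D6-D8 | 36 | 24 × 9/8 = 27 | 300 | +9.9% |

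**Other assumed courses.**
- Exponential fall from 60 at 0.25 per day: carry-forward +0.7%, +3.6% and +9.7%; interpolation +0.1%, +0.6% and +1.9%.
- Flat: a = b, so no error.
- Rising (40 up to D7, 50 at D8, 60 at D9; true AUC 285), with only D8 missing: carry-forward gives 280, which is −5 or −1.8%.
- Bound: the total score runs from 0 to 140 (20 items, 0-7). A single missed D8 can therefore move the AUC by at most 140/4 = 35 points either way, against a maximum AUC of 140 × 7 = 980.

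**Mean AUC.** If 10% of patients (assumed) follow the linear course and have gaps of 1, 2 or 3 days, the mean rises by 0.3, 1.2 or 2.7 points, that is 0.1%, 0.4% or 1.0% of 273.

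**Treatment difference.** The table shows it when every patient in both arms has the same gap.

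| Assumed curves | True | D8 | D7-D8 | D6-D8 |
|---|---|---|---|---|
| Exponential from 60: placebo 0.25/day, active 0.412/day (AUC 30% lower) | 59.8 | 60.4 | 62.2 | 64.7 |
| Linear, active 30% lower on every day | 81.9 | 82.8 | 85.5 | 90.0 |
| Linear from 60: placebo 6/day, active 9.47/day, floored at 0 | 81.9 | 83.3 | 78.1 | 69.4 |

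The first two rows widen throughout. The third widens for one missed day and shrinks for two or three.

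**Unequal missingness.** Suppose one arm has 5-20 percentage points more single missed D8 scores, at 3 points each. The difference moves by 0.15-0.6 points against a 30% effect of 0.30 × 273 = 81.9. With a coefficient of variation of 0.81, power goes from 80.0% to 79.9-79.5%.

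**The case against.** - *Protocol section 8 calls itself a summary and leaves detail to the SAP.* True, and the protocol has no rule when no later score exists, so some carry-forward is unavoidable. But where D9 is available, carrying forward replaces interpolation and does not elaborate it.
- *Few patients are affected.* Plausible. SAP 7.2 refers to daily calls when the questionnaire is not completed, there is a scheduled D8 call, and compensation depends on diary completion (Protocol 7.3.9). Patients who stop early after recovery normally have no later score and are untouched. This limits the size but does not remove the conflict.
- *The per-protocol analysis limits the damage.* In part. If the D8-1 condition in SAP 7.2 means D7 or D8, patients missing both days leave the per-protocol set and only the single-day error stays there. The larger errors remain in the full analysis set.
- *Interpolation brings in off-treatment data.* The last intake is on D8 morning (Protocol 7.4.1), so D9 lies just beyond treatment. A score as late as D15 would be a poor anchor. This stands, and it is why the window should be short.

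A reader might go further and infer that the rule always inflates the AUC, shrinks a real treatment difference and can never favour the device. The documents do not support that. The protocol's statement that 75% of persons improve or resolve within 7 days covers all patients, whereas those with scores after D8 are mainly the ones still sick. The rule applies in both arms, and under two of the three assumed pairs of curves it widens the difference at every gap length.

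**Conclusion.** The contradiction holds. For a patient with a missing D8 and a score soon after it, Protocol 8.9 and SAP 6.4.7 prescribe different primary values, and SAP 12 is silent. That SAP 6.4.7 applies in this case is read from the absence of an exception; the SAP does not say so outright.

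The size is modest. Per patient the error is 1.1%, 4.4% or 9.9% for one, two or three trailing days on the assumed 6-point daily fall; it is nil for flat scores and negative for rising ones. Mean AUC moves by about 0.1-1% under an assumed 10% prevalence. The direction of the effect on the treatment difference is not determined: it depends on the shape of the curves and on missingness by arm, neither of which the documents give. Severity: minor. The case for change is agreement between the documents on the conclusive endpoint, not a demonstrated bias in the result.

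**What to change.** Replace the last sentence of SAP 6.4.7 with:

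*If D8 is missing and a WURSS-21 score is available shortly after D8 (a window fixed before unblinding, for example D9 or D10), D8 is obtained by linear interpolation between the last score before and the first score after D8, as in protocol 8.9. Otherwise the last value before D8 is carried forward.*

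Then:
- list the remaining carry-forward in SAP 12 as a departure from Protocol 8.9, including patients who stopped the diary early after recovery;
- report the primary analysis under the present carry-forward rule as a sensitivity analysis.

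The cost is a few sentences, a few lines of code and one extra table; the data are already collected. The downside is that the interpolated D8 draws on a score recorded just after the last intake.
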